#### **Group 1 Efficacy Endpoint**

Sample size justification is based on data from a recently completed NIAID therapeutic vaccine study of early treated subjects (Protocol 13-I-0141). In the Placebo arm of the therapeutic vaccine study, 80% of subjects would have met the criteria listed in Section 3.1 to restart ART prior to study week 32. Table 2 shows power for ART restart probabilities between 0.20 and 0.30 in the 3BNC117 plus 10-1074 arm. Power is approximately 87% and 80% for ART restart probabilities of 0.20 and 0.24 in the 3BNC117 plus 10-1074 arm.

Table 2. Power shown in row 2 for different ART restart probabilities in the 3BNC117 plus 10-1074 arm (row 1). The restart probability in the placebo arm is assumed to be 0.80.

Restart Prob. bNAb arm	0.20	0.22	0.24	0.26	0.28	0.30
Power	0.872	0.840	0.804	0.765	0.724	0.680

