# **Endpoints:**

The rate of occurrence of grade 3 or higher AEs, including SAEs, that, per standard criteria (see safety Section 12.3.1) are probably or definitely related to the test article.

Number of subjects who experience rebound of plasma viremia and meet criteria to restart ART before study week 28. (Cohort 1)

The number of subjects in Cohort 2 who achieve stable suppression of viremia with 3BNC117 plus 10-1074 by study week 28.

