#### 3 STUDY DESIGN

# 3.1 Description of the Study Design

The proposed trial will be a triple-arm study to examine the effect of 3BNC117 combined with 10-1074 in two groups of HIV-infected individuals. In Group 1, 30 individuals who began ART during primary HIV-1 infection will be randomized 1:1 to treatment with 3BNC117 plus 10-1074 or normal saline placebo. Study staff and participants will be blinded to Group 1 treatment assignments. Efficacy will be measured in this group by comparing the number of subjects in the treatment and placebo arm who meet criteria to restart ART during the ATI-treatment phase of the study (weeks 0-28).

For study Group 2, up to 15 viremic individuals not taking ART will receive 3BNC117 combined with 10-1074. Efficacy will be measured in this group by the proportion of subjects in whom mAb treatment is able to suppress plasma viremia during the treatment phase (weeks 0-28). Study subjects will receive infusions of 3BNC117 (30mg/kg) and 10-1074 (30mg/kg) or placebo (Group 1) at study days 0, Week 2, Week 4, and every four weeks thereafter for up to 24 weeks (Figure 1).

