## Analytical treatment interruption (ATI)

After study day 3, all subjects in **Group 1** will stop ART to determine if treatment with 3BNC117 and 10-1074 can prevent plasma viral rebound. Individuals taking non-nucleoside reverse transcriptase inhibitors (NNRTIs) will switch to a protease or integrase inhibitor-based regimen at least 2 weeks prior to week 0 to ensure that the washout period of antiretroviral agents is roughly equal. During the ATI/Treatment phase of the study, HIV RNA levels and CD4+ T cell counts will be monitored every 2 weeks.

Group 1 subjects will be instructed to restart ART if they meet one or more of the following criteria during the ATI phase:

[figure not shown]
- A confirmed >30% decline in baseline CD4+ T cell count or an absolute CD4+ T cell count <350 cells/mm^3 that is associated with a HIV RNA level >40 copies/ml.
- A sustained (>4 weeks) HIV RNA level of >1,000 copies/mL
- Any HIV-related syndrome (e.g. acute retroviral syndrome, opportunistic infection)
- Pregnancy

Subjects who meet one or more of the above criteria during the ATI/Treatment Phase will not receive additional antibody/placebo infusions and enter the follow-up phase (Figure 1). Subjects who have not met criteria to restart ART by week 28 may continue the ATI and have HIV RNA levels and CD4+ T counts monitored every 2 weeks until they either meet criteria to restart ART or reach study week 64 (see Section 6.4).

Subjects in **Group 2** will have their plasma viremia and CD4+ T counts monitored every 2 weeks and will be removed from the treatment phase of the study if they meet any of the following criteria:

- A confirmed >30% decline in baseline CD4+T cell count or an absolute CD4 cell count <350 cells/mm^3
- A sustained (>4 weeks) 0.5log10 increase in baseline HIV RNA level
- Opportunistic infection
- Pregnancy

Figure 1: Study Outline

\* Placebo for Group 1 only

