# 3.2.2 Secondary Endpoints

Difference between the treatment and placebo arms in the number of subjects in study Group 1 who experience rebound of plasma viremia and meet criteria to restart ART prior to study week 28.

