#### 6.3 ATI/Treatment Phase

Subjects will be administered 3BNC117 and 10-1074/ placebo on study day 0. All subjects in Group 1 will discontinue their ART regimen after study day 3. Subsequent infusions of 3BNC117 and 10-1074/placebo will occur at study Week 2, 4, and every four weeks thereafter until study Week 24 for a total of 8 doses (see Figure 1).

Storage of plasma, serum, and cells may be done at study day 0, Week 2, 4 and every 2 weeks thereafter for the duration of the ATI-Treatment phase. Flow cytometry (including CD4 count) and Plasma HIV viral RNA levels will be done every 2 weeks for the duration of the ATI-Treatment Phase. HIV genotype will be obtained on all samples with HIV viral levels >1,000 copies/ml. For select subjects residing outside the local (Bethesda, MD) area, blood samples for blood draw only visits, may be collected at their local clinics or Quest Diagnostics and sent to the NIH Clinical Center for testing. Samples collected at clinics or at Quest may be labeled with a coded identifier, gender, and date of birth, as required by the local facility.

At infusion visits, the following will be done in addition to the flow cytometry panel and plasma HIV viral level:

- Interval medical history and a targeted physical examination, including weight, vital signs, and a symptom-directed evaluation based on symptoms or complaints reported by each subject
- Assessment of concomitant medications
- Assessment of any new or unresolved AEs/intercurrent illnesses
- Blood collection:
  - CBC with differential
  - Chemistry panels, to include: ALT, AST, ALP, creatinine, total and direct bilirubin, and serum albumin levels
- Serum or urine pregnancy test for women of child-bearing potential (results must be reviewed prior to infusion)
- Optional leukapheresis for research studies will be done at Week 0, 16 and within +/14 days of the week 24 infusion
- HIV transmission risk behavior assessment and counseling

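### Does a placebo restart rate read at week 32 of an earlier study undermine the power figures for a week-28 endpoint?

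*Combined protocol and SAP*

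**What the plan says.** The Group 1 Efficacy Endpoint part of Section 14 takes its planning rate from the placebo arm of Protocol 13-I-0141, where "80% of subjects would have met the criteria listed in Section 3.1 to restart ART prior to study week 32". The Table 2 caption carries the figure over as an assumption: "The restart probability in the placebo arm is assumed to be 0.80". The text then reports: "Power is approximately 87% and 80% for ART restart probabilities of 0.20 and 0.24 in the 3BNC117 plus 10-1074 arm".

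The endpoint closes earlier than week 32. Section 3.2.2 counts Group 1 subjects who "meet criteria to restart ART prior to study week 28", and the Protocol Summary counts those who "meet criteria to restart ART before study week 28". Section 3.1 describes the comparison as covering weeks 0 to 28 and adds: "Subjects who have not met criteria to restart ART by week 28 may continue the ATI". On this trial's clock, Section 6.3 says that Group 1 subjects "will discontinue their ART regimen after study day 3", so study week and time off therapy almost coincide.

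The protocol gives no week-28 rate from the earlier study, no date for its treatment stop and no size for its placebo arm.

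**The concern.** The proportion who have met restart criteria can only grow with time. If 80% is reached by week 32, the proportion by week 28 on the same clock is at most 80%. A lower placebo rate narrows the gap between the arms and reduces power. The stated power at an antibody-arm rate of 0.24 is 0.804, which leaves almost no room: at a placebo rate of 0.79 it is already 0.785. A reader who takes both week numbers as weeks off therapy would therefore conclude that Table 2 is optimistic and that 15 subjects per arm give less than the advertised power. Section 1.2 says the placebo arm is needed because a significant proportion of early-treated people stay suppressed without treatment, so this rate is the central planning input for the comparison.

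**Working it through.** **Inputs.** 30 subjects randomised 1:1, so 15 per arm (Section 3.1). Placebo rate 0.80 and antibody-arm rates 0.20 to 0.30 (Table 2). The protocol does not name the test or alpha behind Table 2. Two-sided Fisher's exact test at 0.05 is inferred because it reproduces the table.

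**Step 1: reproduce Table 2.** Power is the sum of Bin(a; 15, p_placebo) × Bin(b; 15, p_antibody) over all pairs (a, b) with two-sided Fisher p ≤ 0.05.

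| Antibody-arm rate | 0.20 | 0.22 | 0.24 | 0.26 | 0.28 | 0.30 |
|---|---|---|---|---|---|---|
| Table 2 | 0.872 | 0.840 | 0.804 | 0.765 | 0.724 | 0.680 |
| Recomputed | 0.8723 | 0.8402 | 0.8045 | 0.7655 | 0.7237 | 0.6796 |

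All six values agree to within 0.001. The table contains no calculation error.

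**Step 2: compare the two clocks.** Here therapy stops after day 3, so week 28 is 28 × 7 − 3 = 193 days off therapy, or 193 / 7 = 27.6 weeks. Week 32 of the earlier study is day 32 × 7 = 224. The two periods off therapy match if the earlier study stopped therapy 224 − 193 = 31 days (31 / 7 = 4.4 weeks) after its own week 0. These figures are nominal: visits have a window of ±5 days and monitoring is every two weeks.

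- If therapy stopped sooner than that, the matched rate is at most 0.80 and Table 2 is right or optimistic.
- If it stopped at about that point, the rate is 0.80 and Table 2 stands.
- If it stopped later, the matched rate is at least 0.80 and Table 2 is right or conservative.

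The protocol does not say which case applies.

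**Step 3: sensitivity.** Only the placebo rate carries the week-32 label. The antibody-arm rates are hypothetical values with no window attached, so they are held fixed.

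| Placebo rate | Power at 0.20 | at 0.24 | at 0.30 |
|---|---|---|---|
| 0.82 | 0.901 | 0.842 | 0.728 |
| 0.80 (Table 2) | 0.872 | 0.804 | 0.680 |
| 0.78 | 0.840 | 0.764 | 0.630 |
| 0.76 | 0.804 | 0.721 | 0.581 |
| 0.755 | 0.796 | 0.711 | 0.569 |

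The last row is an illustration that assumes a shared clock starting at treatment stop and a constant hazard: 1 − (1 − 0.80)^(28/32) = 1 − 0.20^0.875 = 0.755. The loss against Table 2 is about 8, 9 and 11 percentage points. If instead every placebo restart fell before week 28, the loss is zero.

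**Step 4: how firm is 0.80 in any case?** The size of the earlier placebo arm is not given. Assuming 10 to 20 subjects, the exact 95% interval around 80% runs from 0.44–0.97 (8 of 10) to 0.56–0.94 (16 of 20). Even the move from 0.80 to 0.755 is small against that uncertainty.

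**The case for a change.** The strongest case for a change is that the mismatch is plain on the page and cheap to settle. The sponsor evidently applied this trial's restart criteria to the earlier study's data, so counting again at the matching time off therapy is a small task. Section 14 calls rebound requiring restart the primary efficacy outcome, so its power statement should be traceable. The rule requiring viremia above 1,000 copies/mL for more than four weeks does not by itself explain a four-week offset: that lag sits inside the criteria at both time points, and the protocol does not offer it as the reason.

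Most of this stands. The link between the windows is undocumented, and one sentence would have supplied it. What does not follow is that the rate or the power is wrong. Week labels from two studies do not contradict each other when their starting points may differ. The same retrospective use of this trial's criteria makes a deliberate time mapping possible, although the protocol does not state one. Nor would a recount make power well known, given the sampling uncertainty of a small placebo arm.

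**Conclusion.** No change to the plan is needed. The gap is real but confined to the rationale for a planning figure that the protocol itself labels an assumption. Table 2 is correct for a placebo rate of 0.80, given the inferred two-sided Fisher test at 0.05 with 15 per arm. The documents do not show that 0.80 is wrong at week 28, and they do not fix even the direction of any error. The shared-clock, constant-hazard case would cost about 8 to 11 points of power, but it rests on two assumptions that the protocol does not support. Other readings give no loss or a gain.

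Little depends on the answer. The listed primary endpoint is safety, and Table 1 supports the 30 antibody recipients separately. The Group 1 comparison is a secondary endpoint in an exploratory phase 1 trial. Its endpoint window, its sample size and the analysis of its data stay the same whichever placebo rate applied at planning. A reader can treat Table 2 as conditional on 0.80 and use the sensitivity figures above for other rates.

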#### 15 ETHICS/PROTECTION OF HUMAN SUBJECTS

#### 15.1 Informed Consent Process

Informed consent is a process where information is presented to enable persons to voluntarily decide whether or not to participate as a research subject. It is an on-going conversation between the human research subject and the researchers which begins before consent is given and continues until the end of the subject's involvement in the research. Discussions about the research will provide essential information about the study and include: purpose, duration, experimental procedures, alternatives, risks and benefits. Subjects will be given the opportunity to ask questions and have them answered.

The subjects will sign the informed consent document prior to undergoing any research procedures. The subjects may withdraw consent at any time throughout the course of the trial. A copy of the informed consent document will be given to the subjects for their records. The researcher will document the signing of the consent form in the subject's medical record. The rights and welfare of the subjects will be protected by emphasizing to them that the quality of their medical care will not be adversely affected if they decline to participate in this study.

#### 15.1.1 Non-English-Speaking Subjects

If a non-English-speaking subject is eligible for enrollment, the subject will be provided with the CC Short Written Consent Form for Non-English-speaking Research Participants in the subject's native language and a verbal explanation of the purpose, procedures and risks of the study as described in MAS Policy M77-2, NIH HRPP SOP 12 and 45 CFR 46.117(b)(2). The IRB-approved English consent form will serve as basis for the verbal explanation of the study. The investigator will obtain an interpreter unless the investigator is fluent in the prospective subject's language. Preferably, the interpreter will be someone who is independent of the subject (i.e., not a family member). Interpreters provided by the CC will be used whenever possible. The interpreters will translate the IRB-approved English consent form verbatim and facilitate discussion between the subject and investigator.

The IRB-approved English consent form will be signed by the investigator obtaining consent and a witness to the oral presentation. The CC Short Written Consent Form will be signed by the subject and a witness who observed the presentation of information. The interpreter may sign the consent document as the witness and, in this case, will note "Interpreter" under the signature line. A copy of both signed forms will be provided to the subject to take home.

The investigator obtaining consent will document the consent process in the subject's medical record (CRIMSON), including the name of the interpreter. Further, all instances of use of the CC Short Written Consent Form will be reported to the IRB at the time of annual review. If the CC Short Written Consent Form is used three times or more for the same language, this will be reported to the IRB immediately.

#### Illiterate English Speaking Subjects

As the majority of the subject populations from which the study subjects are drawn are literate, written consent will typically be provided. However, this population does have a small rate of illiteracy, and oral consent will be obtained for illiterate subjects as consistent with NIH MAS Policy M77-2 without separate IRB approval for each specific use. At Continuing Reviews, the NIH IRB will be informed of the number of illiterate subjects who provided consent verbally.

#### 15.2 Subject Confidentiality

All records will be kept confidential to the extent provided by federal, state and local law. The study monitors and other authorized representatives of the Sponsor may inspect all documents and records required to be maintained by the Investigator, including but not limited to, medical records. Records will be kept locked and all computer entry and networking programs will be done with coded numbers only. Clinical information will not be released without written permission of the subject, except as necessary for monitoring by IRB, NIAID, OHRP, or the sponsor's designee.

#### 16 DATA HANDLING AND RECORD KEEPING

#### 16.1 Data Capture and Management

Study data will be maintained in CRIMSON and collected directly from subjects during study visits and telephone calls, or will be abstracted from subjects' medical records. Source documents include all recordings of observations or notations of clinical activities and all reports and records necessary to confirm the data abstracted for this study. Data entry into CRIMSON will be performed by authorized individuals. Corrections to CRIMSON shall be tracked electronically with time, date, individual making the correction, and what was changed.

The investigator is responsible for assuring that the data collected are complete, accurate, and recorded in a timely manner.

#### 16.2 Record Retention

The investigator is responsible for retaining all essential documents listed in the International Conference for Harmonization Good Clinical Practice Guidelines. Study records will be maintained by the PI for a minimum of 3 years and in compliance with institutional, IRB, state, and federal medical records retention requirements, whichever is longest. All stored records will be kept confidential to the extent required by federal, state, and local law. The FDA requires study records to be retained for up to two years after marketing approval or disapproval (21 CFR 312.62), or until at least 2 years have elapsed since the formal discontinuation of clinical development of the investigational agent for a specific indication.

Should the investigator wish to assign the study records to another party and/or move them to another location, the investigator will provide written notification of such intent to OCRPRO/NIAID with the name of the person who will accept responsibility for the transferred records and/or their new location. Destruction or relocation of research records will not proceed without written permission from NIAID/OCRPRO.

# APPENDIX A: AE REPORTED UNDER PROTOCOLS MCA-0906 AND YCO-0899

(YCO-0899 remains blinded)

Adverse Events	No. AEs	No. Mild	No. Moderate	No. Severe	No. of participants
Related to 3BNC117 and 10-	-1074 Infusio	ons			
Malaise/Fatigue	2	2	0	0	2
Upper respiratory infection	2	2	0	0	2
Elevated bilirubin	1	1	0	0	1
Headache	1	1	0	0	1
Hyperthermia	1	0	0	1	1
Nausea	1	1	0	0	1
Transaminitis	1	1	0	0	1
Total related	9	8	0	1	9
Not Related to 3BNC117 and	d 10-1074 In	fusions			
Unnar rachiratory infaction	9	0	0	0	0
Upper respiratory infection Headache	_	9	0	0	9
Urethritis (gonorrhea, or	4	4	0	0	3
mycoplasma)	3	1	2	0	2
Anemia	2	2	0	0	1
Elevated bilirubin	2	2	0	0	2
Intermittent increase in	2	2	U	U	2
direct bilirubin*	2	0	0	2	2
Sore throat	2	1	0	0	1
Vomiting	2	1	1	0	2
Abdominal distension	1	0	0	0	1
Agitation	1	1	0	0	1
Albuminuria	1	1	0	0	1
	1	1	U	U	1
Altered mental status (drug- intoxication related)	1	0	0	1	1
Epistaxis	1	1	0	0	1
Hypoglycemia	1	1	0	0	1
Increased tearing of left	1	1	· ·	Ü	1
eye	1	1	0	0	1
Malaise/Fatigue	1	0	0	0	1
Myalgia	1	0	0	0	1
Nausea	1	1	0	0	1
Shoulder pain	1	1	0	0	1
Stye	1	1	0	0	1
Urinary retention	1	0	0	0	1
Total Not related	39	28	3	3	35
Total AE's	48	36	3	4	44

\* Direct bilirubin level was 0.3 mg/dL (normal range 0-0.29 mg/dL). Level was considered grade 3 according to the DAIDS Toxicity Table, version 2.0.

### **APPENDIX B: STUDY FLOW SHEET**

### Group 1 and 2

Study Point		Screening
		UP TO 8 wk
		Before
Date Range		Enrollment
PROCEDURES / CONSULTS		
Consent		X
ECG	12 LEAD	X
DTM Apheresis Assessment		X
Medical History, Targeted PE,		
Sympton Directed Eval, VS, Wgt,		
Medication Review		Х
Ophthalmologic Exam (within 8		
weeks prior to first study infusion)		X
LABS:		
Pregnancy (Blood or Urine)		Х
CBC with Diff		X
PT, aPTT		X
Creatinine, Total and Direct Bili,		
Serum Albumin		X
HBsAG,		Х
Anti-HCV Antibody & HCV RNA Quant		Х
Urinalysis		Х
RESEARCH LABS:		
(WHBL) Flow Cytometry with CD4+		Х
(Abbott HIV RTPCR) HIV Viral Load		Х
Plasma Storage		Х
Serum Storage		Х
PBMC Storage		Х

### Appendix B continued: Group 1 Infusion / ATI Phase

			Pre-Tx Apheresis																		
Study Point		NNRTI SWITCH	#1	Baseline	ART STOP	Infusion 2	Infusion 3	Blood Draw	Infusion 4	Blood Draw	Infusion 5	Blood Draw		Apheresis #2	Infusion 6	Blood Draw	Infusion 7	Blood Draw	Infusion 8	Apheresis #3	extended ATI Phase
																					If pt has not met Group
														Wk 16							1 ATI Restart Criteria by week 24, Continue to
		> 2 WKS BEFORE	Post Screen & Pre											(Before						+/- 14 days	
Date Range		DAY ZERO	FIRST INFUSION	Day Zero	DAY 4	Wk 2	Wk 4	Wk6	Wk8	Wk 10	Wk 12	Wk 14		Infusion)	Wk 16	Wk 18	Wk 20	Wk 22	Wk 24	after Wk 24	Flowsheet.
Protocol Visit Date																					
PROVIDERS:																					
CM Visit				Х	Telephone note	Х	Х		Х		X				Х		Х		Х		
LIP Visit				X		Х	Х		X		X				Х		X		Х		
PROCEDURES / CONSULTS:																					
Pts on NNRTIs switch to																					
Protease or Integrase inhib		Х																			
Medical History, Targeted																					
PE, Sympton Directed Eval,						.,	.,				.,						.,		٠,		
VS, Wgt, Medication Review				X		Х	Х		X		X				Х		Х		Х		
Assess AEs / Intercurrent				v		v	v				v						v				
illnesses	2L			X		Х	Х		X		X		21	х	Х		Х		Х	х	
APHERESIS	ZL		х		-								2L	X						X	
HIV Transmission Risk				.,		x	.,		x		x				.,		x		x		
Assessment / Counsel				X		Х	Х		Х		Х				Х		Х		Х		
Infusion: (3BNC117 & 10-						.,	.,		.,		.,				.,		.,		.,		
1074) or Placebo				Х		Х	Х		Х		X				Х		Х		Х		
CBC with Diff				X		Х	Х		Х		Х				Х		Х		Х		
				^		^	^		_^		^				^		^		_ ^		
Chem: ALT, AST, AIK Phos,																					
Creatinine, Total and Direct Bili. Serum Albumin				x		x	x		x		x				x		x		x		
				^			^		^								۸.		,		
Pregnancy (POC)- Result																					
must be Neg Before Infusion	Urine			х		x	x		x		x		Urine		x		x		x		
HLA (IF not already done at N				X		Х	Х		Х		Х		Urine		Х		Х		Х		
RESEARCH LABS:	inj			^																	
(WHBL) Flow Cytometry																					
with CD4+				x		x	x	x	x	x	x	х		l	x	x	x	х	x		
(Abbott HIV RTPCR) HIV		<del>                                     </del>		^	†	^	^	_ ^	^	^	^	^			^	_ ^	^	^	_^		
Viral Load				x		х	x	x	x	x	x	х			х	x	х	x	x		
HIV Genotype >1000 VL						X	X	X	X	X	X	Х			X	X	X	X	X		
Plasma Storage				х		Х	Х	X	Х	X	Х	Х			X	Х	X	X	Х		
Serum Storage				X		X	Х	X	Х	X	X	Х		İ	X	Х	X	X	Х		
(PBL Storage) PBMC Storage				Х		Х	Х	Х	Х	Х	Х	Х			Х	Х	Х	Х	Х		
ONLY If PT Cannot apherese	30 mL Hep Syringe	-	Х	•									30 mL Hep Syringe	Х						Х	
ONLY If PT Cannot apherese	50 mL Hep Syringe		Х	•									50 mL Hep Syringe	Х						Х	•
Blood volume will not exceed	current NIH limits	as defined by MAS-	95-9.																		

